There are no additives in the final ropivacaine 800 mL bag that would affect stability beyond that of the commercial product. In order to ensure the sterility of the ropivacaine during the 5 days of use, the following procedure will be used: The final ropivacaine 800 mL bags will be considered medium-risk compounded sterile products (CSP). In lieu of a separate sterility test, USP 797 guidance indicates medium-risk CSPs should have a beyond use date (BUD) of 30 hours when stored at room temperature. To extend the BUD, sterility testing will be performed on each batch of ropivacaine 800 mL bags. Two of the bags in each batch will be tested for sterility using the QT JuniorTM System (Q.I. Medical, Inc., Grass Valley, CA, USA), which utilizes a 0.22-micron filtration set and fluid thioglycollate growth media [22]. The batched bags will remain quarantined before use for 14 days after preparation. On day 14, the QT systems being incubated from the 2 tested bags will be visually inspected for turbidity per the manufacturer instructions. If no turbidity is seen (i.e., negative growth) at day 14, then the batched bags will be released for dispensing for an additional 14 days (i.e., 28 days total from preparation: 14 days quarantined plus 14 days post-release) while being stored at controlled room temperature in the investigational pharmacy until dispensed or expired. Released bags will only be dispensed if the BUD does not extend beyond the planned 5-day therapy for a specific patient. Following the patient-specific dispense, the ropivacaine bag and pump will be connected directly to the nerve block catheter at the time the catheter is inserted, in the same day surgery area immediately after the single popliteal nerve block is administered. The catheter will be infused using a commercially available ambulatory infusion pump consistent with standard clinical care. Infusion will begin immediately after the surgery, when the patient is in the PACU.

Subjects will be contacted by phone each day by the study nurse or other clinical study member. The script to be used for this follow-up is provided in a separate document. This allows monitoring for post-operative analgesic use, toxicity, infection, or other problems related to the use of the pump, and for reminders about when and how to remove the catheter.

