Clinical trial monitoring will be conducted to ensure that the rights and well-being of human subjects are protected, to verify that the reported clinical trial data are accurate, complete and verifiable from source documents and to verify that the conduct of the trial is in compliance with the currently approved protocol/amendment(s), with Good Clinical Practices and with the applicable regulatory requirements.

Safety criteria for removing a subject from the study in the period before the end of the 5-day ambulatory pump use:

Prior to and during the popliteal nerve block and catheter placement: Subjects with a failed peripheral nerve block will not have a catheter placed and will not be included in the study (see Exclusions, below). Subjects will be discontinued and the catheter removed if there is inadequate view of the popliteal nerve under ultrasound guidance, paresthesias that do not resolve before the local anesthetic from the nerve injection takes effect, blood is present in the catheter during insertion indicating possible vascular injury, or one or more signs of local anesthetic systemic toxicity (LAST) (ringing in ears, metallic taste in mouth, lightheadedness, seizure, or cardiac compromise).

During Surgical Procedure and General Anesthetic – Subjects will be discontinued if there are one or more signs of LAST (listed above) or the catheter is inadvertently removed during the operation.

During immediate postoperative period in PACU – Subject will be removed if there are one or more signs of LAST (listed above) or if the catheter is removed inadvertently

After Discharge for period the pump is used: Based on the daily phone contacts, subjects will stop using the pump if there are, signs of local infection(after evaluation by the Acute Pain Service; subject would be called back into the hospital), or one or more signs of LAST (listed above). Subjects who experience paresthesias that cause them discomfort, or weakness that prevents them from participating in physical or occupational therapy, will be asked to return to the clinic for evaluation by an anesthesiologist. If these issues cannot be resolved (e.g. by lowering the dose), these subjects will have the catheter and pump removed. Subjects who must remove the pump early for any reason will be retained in the study for purposes of answering the pain surveys.

Defining and Reporting of Adverse Events:

Adverse event Definitions:

Adverse Event

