Fatigue	No interference with activity	Some interference with activity	Significant; prevents daily activity	ER visit or hospitalization
Myalgia	No interference with activity	Some interference with activity	Significant; prevents daily activity	ER visit or hospitalization

Table 9.4 extracted from: Guidance for Industry, Toxicity Grading Scale for Healthy Adult and Adolescent Volunteers Enrolled in Preventive Vaccine Trials, U.S. Department of Health and Human Services, Food and Drug Administration, Center for Biologics Evaluation and Research, August 2016

Treatment of cardiovascular and neurologic adverse events

- Local anesthetic systemic toxicity
 - Treatment will be initiated as recommended as the American Society of Regional Anesthesia and Pain Medicine, according to the society's checklist

Treatment will include: transfer to intensive care unit setting if not already in intensive care unit, continuous hemodynamic monitoring for at least 24 hours, appropriate airway management with assistance from respiratory therapy and a critical care consultant as needed, cardiovascular stabilization and assistance from a critical care consultant as needed, administration of Lipid Emulsion therapy, as per ASRA checklist in Appendix, Neurology consult for any observed systemic

neurologic toxicity (including change in vision, mental status change, persistent headache, seizure), Cardiology consult for any arrhythmias that persist greater than 30 minutes, beyond initial appropriate medical treatment, or result in hypotension with systolic blood pressure < 80mmHg.

Every adverse event, whether or not thought to be related to study drug, will be recorded and entered into the Medidata Rave® Case Report Form database.

Any medical condition present prior to study enrollment should not be reported as an adverse event, unless the medical condition worsens in severity or seriousness during the study. In this case it may be reported as an adverse event at the discretion of the Investigator.

The Investigator will review each event and assess its severity and relationship to the study treatment.

Criteria for stopping the study early:

Because this is a small study, criteria for stopping the study will not be based on statistical analysis but rather on the occurrence of any of the following serious adverse events in any of the subjects randomized to receive the ropivacaine pumps:

During immediate peri-operative period after pump has been connected:

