 A single serious adverse event of LAST requiring rescue medication, cardiac resuscitation, or transfer to the ICU.

During the 5 day period of ambulatory pump use:

 A single serious adverse event of catheter site infection requiring hospital admission.

 A single serious adverse event of LAST requiring hospital admission.

During the entire study period:

 A single serious adverse event of any life-threatening adverse event deemed possibly related to the use of the ropivacaine pump.

 Two subjects receiving pumps experiencing moderate adverse events of tinnitus and/or metallic taste in the mouth.

11. Data Safety monitoring plan and/or DSMB:

As discussed in section 6, the medical monitor, [name], will review subject's research data and adverse events to ensure patient safety.”

12. Data Analysis:

The primary outcome measure is SEFAS scores at the indicated time points. A secondary outcome measure is use of opioids in the immediate postoperative period.

Each SEFAS response has 5 ordinal response choices scored 0 through 4, with the lowest score (0) representing the most severe disability and the highest total score being 48. If subjects omit a question the score will be re-normalized; however, the Redcap interface will be designed to try to obtain an answer for each question. The Mann-Whitney test will be used to examine differences in the SEFAS scores at each time point. For analysis of SEFAS scores, the pilot study sample size of 20 per group is sufficient for detecting a difference in scores between groups of 9 points with a power of 0.8 and $\alpha = 0.05$ (using the standard deviation obtained from SEFAS use in an ankle surgery study[35]); this score would represent moving up one rank in 3/4 of the questions which would be a functionally meaningful improvement given the 0 – 4 ordinal scale employed. . Patients who are withdrawn from the study due to failure of the initial nerve block (see above) will be considered as screening failures; no follow-up data or questionnaire scores will be obtained. We consider that such a failure is unlikely to have any relationship to the chronic pain outcome we are studying. The same approach will be taken for patients who decide to withdraw from the study, or are withdrawn by the attending surgeon or anesthesiologist, after randomization but before the single shot nerve block procedure.

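### Three neurologic signs that the protocol treats as systemic toxicity are missing from the list of LAST signs that its pump-stopping rule uses

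*Protocol*

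**What the plan says.** Four parts of the protocol bear on this. The SAP sections supplied do not mention LAST, so they offer no further definition.

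- **Section 10, safety criteria for removing a subject.** For the period of block and catheter placement, subjects are discontinued for one or more "signs of local anesthetic systemic toxicity (LAST) (ringing in ears, metallic taste in mouth, lightheadedness, seizure, or cardiac compromise". For surgery, the PACU and the pump period after discharge, the rule refers back to this list with "one or more signs of LAST (listed above".
- **The same section, after discharge.** "Based on the daily phone contacts, subjects will stop using the pump if there are, signs of local infection", and the sentence goes on to add "or one or more signs of LAST (listed above). Subjects who experience paresthesias that cause them discomfort". Discomforting paresthesias, and weakness that prevents therapy, have a separate route: these subjects "will be asked to return to the clinic for evaluation by an anesthesiologist", with removal of catheter and pump if the problem cannot be resolved.
- **Section 10, treatment of cardiovascular and neurologic adverse events.** Under the LAST heading, a neurology consult is required for any observed systemic "neurologic toxicity (including change in vision, mental status change, persistent headache, seizure".
- **Section 10, criteria for stopping the study early.** During the ambulatory pump period, one trigger is "A single serious adverse event of LAST requiring hospital admission".

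Section 6 describes the daily calls in general terms: "This allows monitoring for post-operative analgesic use, toxicity, infection, or other problems related to the use of the pump". It places the call script in a separate document, which was not supplied.

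**The concern.** One section of the protocol describes neurologic toxicity in two ways. The description used to treat LAST names three signs that are absent from the description used to decide when a subject comes off the pump. For most of the five days the subject is expected to be at home, and the person on the daily call is a study nurse or another clinical study member. A caller who hears of visual change or confusion will look to the written criteria and find neither a stop instruction nor an evaluation instruction.

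There is a second consequence for trial conduct. The study can be stopped on one serious LAST event that needs admission. When a single event decides, its classification matters, and the protocol does not say which description of LAST the criterion uses.

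**Working it through.** No statistical quantity is involved. The check sets the passages side by side.

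**Step 1. Match the neurologic signs named under treatment to the written at-home rules (both in section 10).**

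| Sign named in the treatment text | On the five-item LAST list? | Other written at-home trigger in the removal criteria? |
|---|---|---|
| Change in vision | No | No |
| Mental status change | No | No |
| Persistent headache | No | No |
| Seizure | Yes | Not needed |

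Four signs are named and one is shared, so 4 − 1 = 3 have no written at-home trigger.

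**Step 2. Is the five-item list open or closed?** Its parenthesis carries no word such as *including* or *e.g.*, and the later phases refer back to the items as listed. It therefore reads as closed. The treatment list does open with *including*, so it gives examples. The comparison is informative in one direction only: a sign named under treatment and absent from the closed list is a gap, while a sign on the closed list that the treatment text does not name is not.

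**Step 3. Could the three signs reach action by the evaluation route?** That route names paresthesias and weakness only. None of the three signs is either of these.

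**Step 4. Apply the study-stopping criteria to a test case.** Suppose a pump subject is admitted during the infusion with altered mental status that is thought to be drug-related.

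- If LAST means the five listed signs, the LAST admission criterion is not met.
- If LAST includes the neurologic toxicity named under treatment, it is met. The risk discussion earlier in section 10 supports this reading, since it describes systemic toxicity broadly, as CNS symptoms or cardiac symptoms.
- The criterion for a life-threatening event possibly related to the pump need not apply, because an admission is not by itself life-threatening under the protocol's definition.
- The two-subject criterion concerns tinnitus and metallic taste, and does not apply.

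The same event can thus meet or miss the trigger, depending on a judgement that the text does not settle.

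**The case against.** The strongest reply is that the two lists do different jobs. One names signs that require discontinuation. The other says when to call Neurology, within a paragraph on treating toxicity that has already been recognised. It does not say that an isolated headache reported by phone is LAST. This is fair, and it limits the point. It does not remove it, because the treatment text sits under the LAST heading and calls these signs systemic neurologic toxicity, and nothing explains why they are absent from the signs that stop the pump.

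A reader might infer that a subject with one of these signs must, by rule, go on infusing. The documents do not support that. The removal criteria say when a stop is required and nowhere direct continuation, and they foresee early pump removal for other reasons.

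A reader might also infer that the stopping list is the only protection at home. That is not supported either:

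- Section 6 has the daily calls monitor for toxicity in general, and the risk discussion in section 10 describes daily contact in similar terms.
- Section 15 lets the orthopedic surgeon or anesthesiologist withdraw a subject at their discretion.
- Section 10 has the investigator review every adverse event for severity and relationship to treatment.
- Section 6 has a medical monitor who reviews adverse events and can halt enrollment.

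These routes stand. They rely on judgement, and none tells the caller when to escalate.

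On study stopping, it can be said that the criterion rests on a diagnosis of LAST and not on a symptom list. That also stands, and it is why the classification is described here as left to judgement and not as contradictory.

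**Conclusion.** The mismatch is real and holds in a limited form. Three of the four neurologic signs that the protocol names under LAST treatment have no written stop or evaluation trigger in the at-home rules. Whether an admission with such a sign counts toward the LAST stopping criterion is left to judgement.

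The conclusion rests on reading the five-item parenthesis as closed, which its wording and the back-references support. It also rests on the protocol text alone. The call script and the society checklist that the treatment text places in an appendix were not supplied, and either may already cover these signs in practice. How often the gap would matter cannot be estimated from the documents.

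Because other routes to action exist, this is not a defect that leaves subjects unprotected. It is still more than missing detail: a stated safety rule does not cover signs that the protocol itself calls toxicity, and the correction is specific and cheap. The amendment should be made.

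**What to change.** The study clinicians and the medical monitor should reconcile the removal criteria with the LAST treatment text in section 10 and agree one description of LAST signs. The discontinuation and pump-stopping rules and the LAST items in the early-stopping criteria should then refer to that description. If the two passages are meant to differ because they serve different purposes, the protocol should say so and state how a sign named only under treatment is handled when it is reported on a daily call. The phone script should be checked against the result. Which signs belong in the description, and what action each calls for, is for the clinicians to decide.

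The cost is a wording amendment and possibly a matching edit to the script. If the agreed description is longer than the present list, there may be a few more pump interruptions. Sample size and outcome analyses need no change.

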changes in medical practice that may reduce development of chronic pain conditions after trauma and surgery.

6. Study design:

This is an investigator-initiated, single-center, prospective, non-blinded, randomized pilot study. We are requesting authorization to enroll up to 60 patients to allow for 40 evaluable subjects.

Adults undergoing surgery for open reduction and internal fixation for traumatic ankle fracture will be invited to participate in the study comparing the 2 forms of nerve block. All patients are currently given the option of popliteal nerve block (single injection of ropivacaine given just prior to surgery), which helps provide pain relief in the immediate postoperative period; the surgery itself is done under general anesthesia. Participants who have agreed to have the single shot procedure will be randomized into the control group (standard-of-care single injection of local anesthetic just prior to surgery) or experimental group (standard-of-care single injection plus 5 day ambulatory popliteal nerve block).

Standard-of care procedures for placement of the popliteal nerve block are as follows: The blocks are performed in the Same Day Surgery (Pre Op Holding Area), by Anesthesia Residents with direct supervision by Anesthesia Attending Faculty. All residents performing blocks are at training level PGY2 (second year resident) or above. Monitors utilized for block placement will be EKG, SpO₂, and Non Invasive Blood Pressure monitor. Standard ASA monitors are on the patient for the block. Supplemental oxygen is in every room as needed. A Code Cart is readily available in SDS and PACU for resuscitative measures if needed (rescue medications, ACLS Medication). A Lipid rescue agent (20% Intralipid solution) is available at all times in the OR Pharmacy (right next to Same Day Surgery). A difficult airway cart is available in PACU and SDS as well for any need for managing the airway. If there is a minor vascular injury (inadvertent needle puncture of the artery) the needle is repositioned prior to the injection. The single injection for popliteal nerve block generally consists of 20 ml of 0.5% ropivacaine. As part of standard care, patients sign a separate clinical consent form specifically for lower limb nerve block procedures.

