The treatment will be open label due to the impracticality of blinding the physician or patient to the presence of local anesthetic in the 5 – day pump and the ethical barriers to subjecting patients to implantation of a catheter and empty or saline pump with no benefit to them. Per standard of care, patients in both the

experimental and control groups will also have other oral pain medications prescribed for use as needed.

Additional data routinely obtained for clinical purposes will also be collected including demographic variables, opioid use in the PACU, pain medications prescribed at discharge, and type of ankle fracture. Standard database templates will be used to record information from the medical record where appropriate.

The patients randomized to the 5 day pump group will be undergoing an experimental procedure: ambulatory pumps for peripheral nerve block (including popliteal) are already successfully used in our clinics (with patients taking the pumps home and doing the removal of the catheter there) in the context other surgeries; but this is not routinely done for ankle fracture surgery nor for the indication of preventing development of chronic pain. In addition, normally the pumps are used for a shorter period of time.

The standard follow-up appointments with the orthopedic surgeons following ankle surgeries are at 10 - 14 days, 5 – 6 weeks, and 3 – 4 months. These visits will allow for monitoring of unexpected problems in patients receiving the pumps. In order to have consistent monitoring, a single orthopedic doctor will review the charts of all the enrolled patients in the experimental group on a regularly scheduled basis (at least monthly). As per our grant proposal patient charts will be reviewed for up to 3 months after use of the pumps. In addition, [name] will act as medical monitor for the study. He will review subject's research data and adverse events to ensure patient safety. The medical monitor will have the power to temporarily or permanently halt enrollment, if it is deemed that patient safety is compromised.

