Subjects will be contacted at approximately 14 days and 3, and 6, and 12 months following the surgery to complete a pain questionnaire, the SEFAS (Self-Administered Foot and Ankle Questionnaire). The SEFAS is designed to evaluate disorders of the foot and ankle. It does not require physician input, and a study of its use after surgery found it to be a valid, reliable, and responsive patient-oriented outcome measure [23]. It consists of 12 questions focusing primarily on pain and its functional impact on daily life activities [24], meeting the new recommendations to use functional and patient centered outcomes in clinical research on pain [25]. Subjects will also be asked to provide information about their medication use including pain medications, at each of these time points. The consent form is structured to allow access to the medical records to obtain information about relevant clinical variables such as medications prescribed, complications, and diagnoses of chronic pain conditions.

The follow-up contacts to obtain questionnaire data will be made according to the subject's preferred contact method. Surveys will be available for subjects to complete on the internet, or via paper copy mailed to them or via telephone, as per their preference. For survey time points that coincide with the orthopedic

doctor's follow-up, [name], the orthopedic surgeon involved with the study, may administer the survey.

7. Research data collection/study procedures:

Encounters: Consent and randomization will occur before the ankle surgery. For subjects in the experimental group, the catheter will be inserted just before surgery in conjunction with the standard-of-care single shot popliteal nerve block procedure, and local anesthetic perfusion will begin immediately after the surgery. All subjects will be contacted via their preferred method of contact to complete the pain survey (SEFAS) at 2 weeks, 3 months, 6 months, and 1 year after the surgery. Information about current pain medication use will also be collected at each of these time points.

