One primary risk of the ambulatory pump is vascular puncture allowing the local anesthetic to enter the general circulation. Ultrasound guidance and (if also needed) peripheral nerve stimulation techniques are routinely used for inserting the catheters in order to minimize this risk[29]. Vascular puncture would likely occur during the standard-of-care initial single shot nerve block, not during the experimental 5 day pump procedure; and would be detected in the hospital setting with rescue medications and procedures available. A second source of risk is systemic toxicity even from a properly placed nerve block, leading to CNS symptoms including seizures or cardiac symptoms. Previous studies of long term regional nerve blocks in trauma patients have demonstrated that systemic ropivacaine levels start to decline after 3 days, and ropivacaine infusion even lasting much longer than the proposed 5 days does not lead to toxic levels of the drug in plasma [12]. Military medicine studies have demonstrated the safety and efficacy of regional anesthesia for combat wounds, especially for managing surgical and acute postoperative pain [12, 13]. As described in these studies, many wounded soldiers have had regional anesthesia lasting at least 5 – 7 days, without serious anesthetic complications, albeit but under field conditions in which the conditions and effect on chronic pain development could not be rigorously controlled. Some of the exclusion criteria are based on higher risk of toxicity per the drug manufacturer's information [30]. Another risk is of infection of the catheter site which rarely may lead to systemic infection. This risk increases with duration of the catheter use. In a study in orthopedic surgery patients using similar mean duration to what we propose [31] the overall risk of local inflammatory signs was 3%.

More Common Risks of peripheral nerve block and continuous peripheral nerve block:

- Bleeding/blood aspiration (0.4%) [32]
- Local Infection 0 – 3% [29, 31]
- Paresthesia (short term; 0.5% - 1.5%) [31-33]
- Inability to perform injection (see section 14 below)
- Ineffective block (see section 14, below)

Extremely Rare Risks:

- Nerve damage (short duration)
- Muscle atrophy
- Worsening of pain

Permanent or long-lasting nerve damage 4-7/10,000 blocks[27]
Local anesthetic systemic toxicity- (0.7 per 10,000)
Cardiac arrest (<1/100,000 with no deaths in several studies of >100,000 peripheral nerve blocks) [29, 34]

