Adverse event means any untoward medical occurrence associated with the use of a drug in humans, whether or not considered drug related.

An adverse event (also referred to as an adverse experience) can be any unfavorable and unintended sign (e.g., an abnormal laboratory finding), symptom, or disease temporally associated with the use of a drug, and does not imply any judgment about causality. An adverse event can arise with any use of the drug (e.g., off-label use, use in combination with another drug) and with any route of administration, formulation, or dose, including an overdose.

Suspected Adverse Reaction

Suspected adverse reaction means any adverse event for which there is a reasonable possibility that the drug caused the adverse event. For the purposes of IND safety reporting, 'reasonable possibility' means there is evidence to suggest a causal relationship between the drug and the adverse event. A suspected adverse reaction implies a lesser degree of certainty about causality than adverse reaction, which means any adverse event caused by a drug.

Adverse Reaction

An adverse reaction means any adverse event caused by a drug. Adverse reactions are a subset of all suspected adverse reactions where there is reason to conclude that the drug caused the event.

Unexpected

An adverse event or suspected adverse reaction is considered "unexpected" if it is not listed in the investigator brochure or is not listed at the specificity or severity that has been observed; or, if an investigator brochure is not required or available, is not consistent with the risk information described in the general investigational plan or elsewhere in the current application, as amended.

Serious

An adverse event or suspected adverse reaction is considered "serious" if, in the view of either the investigator or sponsor, it results in any of the following outcomes: Death, a life-threatening adverse event, inpatient hospitalization or prolongation of existing hospitalization, a persistent or significant incapacity or substantial disruption of the ability to conduct normal life functions, or a congenital anomaly/birth defect. Important medical events that may not result in death, be life-threatening, or require hospitalization may be considered serious when, based upon appropriate medical judgment, they may jeopardize the

patient or subject and may require medical or surgical intervention to prevent one of the outcomes listed in this definition.

Life-Threatening

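### Recording a worsened pre-existing condition as an adverse event is left to an unblinded investigator's discretion, against the protocol's own rule that all adverse events are recorded

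*Protocol*

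**What the plan says.** All the reporting text is in Protocol section 10, under Defining and Reporting of Adverse Events and the paragraphs that follow its grading tables.

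- Definition: "Adverse event means any untoward medical occurrence associated with the use of a drug in humans, whether or not considered drug related".
- General rule: "Every adverse event, whether or not thought to be related to study drug, will be recorded" and entered in the case report form database.
- Next paragraph: a condition that predates enrolment is not to be reported as an adverse event "unless the medical condition worsens in severity or seriousness during the study". It continues: "In this case it may be reported as an adverse event at the discretion of the Investigator".
- The investigator then reviews each event for severity and relationship to treatment.

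Protocol section 6 describes the trial as a "single-center, prospective, non-blinded, randomized pilot study" and justifies this by the "impracticality of blinding the physician or patient". The risk list in section 10 includes "Worsening of pain" among the extremely rare risks of the block; it does not name the ankle.

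**The concern.** The discretion has no criteria attached, and it expressly reaches worsening that becomes serious. The person who exercises it knows whether the subject has a pump. Every subject enters with a fractured ankle awaiting surgery, so ankle pain will commonly predate enrolment, and its worsening can fall under the optional rule. An investigator could follow the protocol to the letter and still produce adverse-event counts that are selective by arm.

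This matters because the pilot is meant to inform a larger study and because safety oversight works partly from adverse-event records. An event that is never entered as an adverse event receives no severity grade, no seriousness classification and no causality assessment.

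**Working it through.** The point turns on wording, and the plan gives no figure to reproduce. The check sets the passages side by side.

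**1. Can the two rules both hold?** The general rule covers every adverse event. The definition covers any untoward occurrence and has no exception for a condition that was already there. Both arms receive ropivacaine (the control arm in the single injection), so the definition applies to both. Worsening of a prior condition therefore falls inside the definition and must be recorded under the general rule, yet it is optional under the next paragraph. The two rules cannot both be followed as written.

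**2. Does the option reach serious events?** Yes, since worsening in seriousness is named. The protocol's own tables give an example. In the toxicity scale, local pain leading to an emergency visit or hospital stay is Grade 4, and the definition of serious includes inpatient hospitalization. An admission for worsened ankle pain would be serious, but recording it would be optional.

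**3. What is captured anyway, in both arms?**
- Numerical pain ratings in the recovery room (Protocol section 7).
- SEFAS: subjects "complete the pain survey (SEFAS) at 2 weeks, 3 months, 6 months, and 1 year after the surgery", with pain medication asked at the same times.
- Pain status at each orthopedic follow-up, and chronic pain diagnoses at one year (SAP section E).
- The medical monitor reviews research data as well as adverse events (Protocol sections 6 and 11).

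These sources have limits. No pre-operative SEFAS is planned, so SEFAS cannot show worsening within a patient from before enrolment. Clinic pain status has three levels. None of these sources carries grade, seriousness or causality. SAP section E has no sensory or motor-loss variable, and the mock tables in SAP section I include no adverse-event table. The scheduled monthly chart review by one orthopedic doctor covers the experimental group only (Protocol section 6), so it cannot balance the arms.

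**4. Which stopping criteria could be touched?** Protocol section 10 lists these for subjects randomized to pumps:

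| Criterion | Could it be a worsened prior condition? |
|---|---|
| Systemic toxicity, peri-operative or during pump use | No; the block comes after consent |
| Catheter-site infection with admission | No; the catheter comes after consent |
| Life-threatening event possibly related to the pump | Yes |
| Two pump subjects with moderate tinnitus and/or metallic taste | Yes; prior tinnitus is not an exclusion in Protocol section 14 |

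If exactly two pump subjects qualify under the last criterion and one has worsened prior tinnitus that is not reported, the count is 2 − 1 = 1 and the criterion is not met. Pain, numbness and weakness are not named as criteria.

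**5. Size.** With 40 to 60 subjects split equally, a pump arm has 20 to 30. One omitted case changes an observed rate by 1/30 = 3.3 to 1/20 = 5 percentage points. That is only the weight of one subject in a small arm. It does not say how often omission would happen or whether it would differ by arm, and nothing in the documents allows either to be estimated.

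**The case against.** The strongest reply is that little is lost. Pain and function are the primary outcome, collected in both arms whatever the adverse-event decision, and the medical monitor sees research data. That stands, subject to the limits listed above. A reader might infer that worsening ankle pain would go unrecorded altogether; the documents do not support that.

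Other stronger readings also fail:
- A reader might infer that the listed risk of worse pain is always worsening of a prior condition. The risk list does not name the ankle. Pain from nerve injury or at the catheter site would be new and would fall under the mandatory rule.
- A reader might infer that block-related numbness or weakness escapes in the same way. No passage says that subjects have such deficits at entry. New deficits are not covered by the option, and section 10 sends troublesome paresthesias or weakness during pump use for evaluation.
- A reader might infer that any serious worsening drops out of stopping review. Only two criteria are exposed, and the definitions let the sponsor as well as the investigator judge an event serious or life-threatening.

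It can also be argued that reporting means onward notification and that everything is still recorded. The text draws no such distinction, and the sentence concerns what counts as an adverse event.

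A practical objection has force. The only pain row in the toxicity scale makes any narcotic use Grade 3, and opioids are given postoperatively as needed. Unqualified mandatory recording could turn routine postoperative pain in both arms into Grade 3 events. This narrows the fix but does not remove the need for it.

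**Conclusion.** The point holds as a conflict within Protocol section 10. One paragraph requires every adverse event to be recorded. The next makes recording of worsening, including serious worsening, optional for an investigator who knows the allocation. The adverse-event record can therefore be incomplete, and incomplete differently by arm, without any breach of the protocol.

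The consequence is moderate. What can be lost is recording, grading and causality assessment as an adverse event; the pain data themselves remain. No primary or secondary outcome is affected, and two stopping criteria are exposed only in particular circumstances. The conclusion assumes that reporting an event as an adverse event means entering it in the adverse-event record, and that some subjects will have prior conditions that can worsen, which the fracture makes likely. It does not assume that any investigator would use the discretion selectively.

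**What to change.** In Protocol section 10, replace the sentence "In this case it may be reported as an adverse event at the discretion of the Investigator" with: *Such worsening will be recorded as an adverse event.* State that this applies identically in both arms and that the investigator assesses severity and relationship as for any other event.

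Add a sentence for expected pain: *Expected postoperative ankle pain already captured by the PACU scores and SEFAS is not recorded separately unless it meets the protocol's definition of serious or is judged possibly related to the block, catheter or pump.* This still leaves an unblinded judgement of relatedness, but a narrower one with stated criteria, and it no longer covers serious events.

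The cost is two sentences in the protocol and a few more adverse-event forms. The second sentence keeps routine postoperative pain from swelling that number. Treatment, visits and the efficacy analysis do not change.
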